6.2.2 Enrollment, Baseline, and/or Randomization

Enrollment

Subjects are considered enrolled once the informed consent document has been signed and randomization has occurred. Only one written informed consent document will be used, as we have

requested a partial HIPAA waiver for screening.

Baseline Assessments

- Pre-Treatment Pain Intensity Assessment (Pre) using a 0-10 NRS^{58,59} will be collected: a) for acupuncture patients, before administration of acupuncture; b) for usual care patients who receive a pain medication order within 60 minutes (+/- 15 minutes) of being roomed, just before or at administration of pain medication; or c) for usual care patients who have not received a medication order within 60 minutes (+/- 15 minutes) of being roomed, at 60 minutes (+/- 15 minutes). The collection time window of 60 minutes was based on median time from being roomed to first pain medication (54 minutes) using data obtained from the ANW ED pilot study (See Figure 1). Pre-treatment pain assessments will be timed to be completed immediately prior to the administration of either the acupuncture or usual care treatments.
- Anxiety scores using a 0-10 NRS^{58,59}
- Expectancy will be measured with the following questions.
 - By the end of the treatment period in the ER, how much improvement in your pain symptoms do you think will occur?
0% 10% 20% 30% 40% 50% 60% 70% 80% 90% 100%

Now, please close your eyes for a few moments and try to identify what you really feel about the treatment and its likely success. Then answer the following questions:

- At this point, how much do you really feel that the treatment will help you to reduce your pain symptoms?
1 2 3 4 5 6 7 8 9
Not at all Somewhat Very much
- By the end of your treatment period in the ER, how much improvement in your pain symptoms do you really feel will occur?
0% 10% 20% 30% 40% 50% 60% 70% 80% 90% 100%

Randomization

Immediately after screening, obtaining informed consent from eligible patients, and collecting baseline data, the study staff will randomize patients to either Acupuncture or Usual Care.

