9.5 Outcomes

Implementation and Treatment Outcomes

All data analyses will be preceded by extensive data checking and verification to identify and resolve the reasons for missing values, inconsistencies, and out-of-range values. Although we anticipate little missing data based on our experience, we will carefully examine whether missingness is completely at random, at random or informative. Models proposed for analysis can handle incomplete data but do

require at least that missingness be at random. Descriptive statistics of primary outcomes: pain intensity change scores for Pre-Treatment to Post-Treatment and Pre-treatment to ED Discharge as well as secondary outcomes will be conducted to assess their distribution overall and by sites as well as demographic characteristics (e.g. sex, age group, race, household income, pain location among others). The variables will be summarized using descriptive statistics (sample size, mean, standard deviation, median, minimum, and maximum) for continuous variables and by the number and percentage of patients for categorical variables. We will report 95% exact confidence interval of median⁸³ for the key continuous variables and 95% exact binomial confidence interval⁸⁴ for categorical variables. All assessments will include sex as a biological variable as described below.

Feasibility of Recruitment and Retention

We will assess recruitment rates (# enrolled / # eligible), pace of accrual, data completeness, and retention at each data collection point, overall and across sites. We will assess variables across different patient groups (including age, race, sex), and across the study arms. Provider adoption will be assessed by the proportion of their eligible patients that clinicians approve for study participation. We will assess variables across different provider characteristics (including age, race, sex), and across the study sites. Completeness of data collection and retention at each time point: we will also track completeness of data collection, and patterns and proportions of missing data at each time point. We will compare these proportions overall and across sites and by demographics as described above.

Acceptability

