9.6 Data Analyses

Aim 2: Conduct a feasibility RCT to examine the feasibility of data collection, intervention implementation and treatment outcomes overall and across sites.

Aim 2a. Evaluate the feasibility of research procedures, including data quality completeness, and participant recruitment and retention, using study records

Overall Approach. Using study records and administrative data we will track recruitment (proportion of eligible patients recruited), document recruitment rates (time to recruit intended sample), and rates of loss to follow up. Data collection forms collected at each time point will be evaluated for quality and completeness. In addition, all quantitative data analyses will be preceded by extensive data checking and verification to identify and resolve the reasons for missing values, inconsistencies, and out-of-range values. Although we anticipate some missing data based on our experience, we will carefully examine whether missingness is completely at random (MCAR), at random (MAR) or informative (MNAR).

Models proposed for analysis can handle incomplete data but do require at least that missingness be at random. Modelling will consider using multiple imputation techniques of covariates to reduce potential biases. To assess recruitment, we will track the number of eligible patients presenting to the ED and the proportion who agree to participate. Basic demographics and presenting complaint will be collected for all eligible patients, allowing us to identify subgroups who are more or less likely to participate. Similarly approaches will be used to assess rates of loss to follow up at all data collection points. We will assess variables across different patient groups (including age, race, sex), and across the study arms as well as overall and by sites.

Aim 2b. Evaluate the implementation of the acupuncture intervention, using both quantitative data (study records, stakeholder surveys) and qualitative data (interviews and observations).

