Overall approach. We base our selection of implementation outcomes on the synthesis and recommendations outlined by Proctor et al in their authoritative 2011 paper.⁸⁶ We include all of the early phase outcomes, excluding cost, proposed in this widely cited framework, including: Feasibility (“practicability”), provider adoption, perceptions of appropriateness, acceptability, and treatment fidelity. These will be assessed both quantitatively and qualitatively. In addition to implementation outcomes, we will also examine implementation processes, strategies, stakeholder experiences, and barriers and facilitators to implementation using both qualitative interviews and real-time observations. For a list of implementation constructs, variables, and data sources, see Table 1.

Table 1: Implementation Variables and Sources

Construct	Variable	Data Collection/Source
Outcomes		
Feasibility		
• Recruitment • Uptake	# recruited patients / # eligible # completed sessions /# recruited	Study records Provider assessment, real-time observations, qualitative interviews
Adoption	# approved / # recruited	Study records
Appropriateness	Suitability for ED setting	1 item survey, qualitative interviews
Acceptability	Satisfaction/helpfulness	1 item survey, qualitative interviews
Fidelity	Adherence to Responsive Manualization	[name] reviews study records and discusses with study acupuncturists
Stakeholder strategies	Processes and steps taken	Qualitative Interviews
Barriers and facilitators	Strengths/weaknesses of the program Contextual influences at patient, provider, local, and institutional level	Qualitative interviews/structured observation

Aim 2b1. Assess Implementation outcomes: feasibility, adoption, appropriateness, and acceptability.

Feasibility is defined as the degree to which AC can be successfully implemented in the ED setting. This is operationalized as **recruitment** (see Aim 2a); and **uptake** (the proportion of recruited patients who receive a complete AC session, measured by a single question assessment: “*Did patient xx receive a completed treatment session at this visit?*”). Feasibility of the study will also be assessed qualitatively, through stakeholder interviews focusing on barriers and facilitators to implementation, and real-time observations of the uptake of the intervention in the ED setting. For a description of qualitative data collection and analysis, see section 2b2 below.

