Provider adoption is defined as the intention to engage with the innovation/intervention. This is operationalized as the proportion of an ED physician’s recruited patients who are approved for study participation. As elsewhere, we will assess variables across different provider characteristics (including age, race, sex), overall and across the study sites to assess group differences in this outcome and those below.

Perception of appropriateness is defined as the perceived **suitability** of the intervention to the ED setting. ED providers will be asked: “*To what degree do you view the acupuncture intervention as useful or suitable for this ED setting?*” (1-very appropriate—5-Very inappropriate); Perceptions of appropriateness will also be explored through qualitative interviews.

‘Acceptability’ is defined as perceptions of the palatability of an innovation, or satisfaction by stakeholders with aspects of an innovation. It is more specific than overall satisfaction with a service.⁹⁹ For this study, acceptability among ED staff is operationalized in our quantitative assessment as satisfaction with the acupuncture intervention as delivered in the ED setting. **Providers** will answer two questions regarding their general opinion about acupuncture: “Do you view acupuncture in general as an appropriate intervention for the ED setting?” Likert scale (1-very appropriate—5-Very inappropriate) and “Do you view acupuncture in general as helpful in managing patient pain in the ED?” Likert scale (1-Very helpful—5- Not at all helpful). And two questions regarding the delivery of ACUITY study in the ED: “Were you satisfied with how the ACUITY acupuncture intervention was delivered in your setting?” Likert scale (1-Very satisfied—5-Very dissatisfied) and “Did the ACUITY project impose a burden on ED staff in your setting?” Not a burden, Somewhat of a burden, Moderate burden, Extreme burden.

Acceptability of the intervention will also be explored in depth in semi structured stakeholder interviews.

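### Section 9.6 divides completed acupuncture sessions by patients of both arms, so full delivery reads as about 50%; separately, provider adoption has conflicting denominators in 9.5 and 9.6

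*Combined protocol and SAP*

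**What the plan says.** **Uptake.** Section 9.6 defines it twice. Aim 2b1 gives "the proportion of recruited patients who receive a complete AC session", to be captured by a single question on whether the patient had a completed session. The Uptake row of Table 1 gives "completed sessions /# recruited".

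**Who counts as recruited.** Aim 2b1 refers back to Aim 2a, which states: "we will track the number of eligible patients presenting to the ED and the proportion who agree to participate". Section 9.5 writes the same rate with enrolled patients on top: "We will assess recruitment rates (# enrolled / # eligible". Section 6.2.2 fixes that term: "Subjects are considered enrolled once the informed consent document has been signed and randomization has occurred". The précis uses recruited for all 150 patients.

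**Provider adoption.** Section 9.5 says: "Provider adoption will be assessed by the proportion of their eligible patients that clinicians approve for study participation". In Section 9.6 the Adoption row of Table 1 reads "approved / # recruited", and the prose takes the share of a physician's "recruited patients who are approved for study participation".

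**Sequence of events.** Under Section 4.3 the provider signs the approval form first, and staff approach the patient for consent afterwards. In Section 3 of the Appendix B screening form, a missing or unsigned form ends the process.

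**The concern.** Sections 3 and 5.1 accept that ED workflow will leave some acupuncture-arm patients untreated. Uptake is the quantitative measure that should show how many. With usual-care patients in the denominator it cannot: they add to the count below the line and can never add to the count above it. A reader who sees about 50% would conclude that half the treatments failed when all were delivered. The planned exact interval would also sit around the wrong quantity.

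Adoption should show whether ED clinicians let their patients into the study, compared across provider characteristics and sites. That comparison needs a denominator fixed before the clinician decides. A denominator of enrolled patients is fixed after the decision, so the measure loses its content.

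The trial exists to refine procedures for a larger RCT, so these two measures bear directly on what it is meant to teach.

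**Working it through.** The plan states no expected value or target for uptake or adoption, so there is no planned figure to reproduce.

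**Inputs**
- 150 patients, 50 per site (précis; 9.2). The 15 pilot patients are left out.
- Two arms in permuted blocks of 2 and 4 with approximate balance (4.3). I infer 1:1 from this, hence 75 per arm; no ratio is written for this trial.
- At most one session per acupuncture-arm patient (5.1).
- Consent: 46 of 59 eligible patients in the pilot RCT (2.2), and 50% as the plan's conservative case (9.5).
- Exact binomial 95% intervals, as named in 9.5 (Clopper–Pearson).

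**Uptake**

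As written, uptake = completed sessions / 150. For the arm that can be treated, uptake = completed sessions / 75.

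| Completed sessions | Over 75 (95% CI) | Over 150 (95% CI) |
|---|---|---|
| 75 | 100% (95.2–100%) | 50.0% (41.7–58.3%) |
| 68 | 90.7% (81.7–96.2%) | 45.3% (37.2–53.7%) |
| 60 | 80.0% (69.2–88.4%) | 40.0% (32.1–48.3%) |

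At one site with 25 of 50 patients in acupuncture, 23 sessions are 23/25 = 92.0% (74.0–99.0%) but read 23/50 = 46.0% (31.8–60.7%).

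The ceiling depends slightly on chance imbalance. An incomplete block of 4 leaves the arms at most 2 patients apart.
- Single list: 74/150 to 76/150 = 49.3% to 50.7%.
- Blocked within site: 24 to 26 of 50 at each site, so 72/150 to 78/150 = 48.0% to 52.0%.

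**Adoption, reading recruited as enrolled**

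Take one provider who approves 18 of 20 presented patients (90%) and another who approves 10 of 20 (50%). These two are illustrations.
- *9.6 prose*: approved patients among enrolled patients. Nobody is enrolled without approval, so both providers score 100%.
- *Table 1*: approved / enrolled. Assume consent among approved patients equals the quoted rate *c*. Then enrolled = *c* × approved, and the ratio is 1/*c*. At pilot consent this is 59/46 = 128%; at 50% it is 1/0.50 = 200%. The approval rate cancels, so both providers get the same score and the ratio tracks patient consent.

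**Adoption, other readings**
- If recruited meant pre-screened, the 9.6 ratio would be usable. That contradicts Aim 2a and the Recruitment row of the same table, where recruited patients are the numerator over eligible ones.
- In 9.5, eligible is workable if it means eligible before sign-off. The sign-off form in 6.2.1 makes eligibility depend on the provider, and the screening form records a status per the ED provider. If eligible means after sign-off, 9.5 also gives 100%.

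**The case against.** The uptake wording may only be loose. It sits under the aim of evaluating the acupuncture intervention, and the completed-session question makes little sense for a usual-care patient. An analyst might restrict to the acupuncture arm without being told. That is plausible, but no text says so, and two matching definitions name the wider group. The sentences about comparing across study arms concern recruitment and retention, and do not restrict uptake.

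Fidelity overlaps with uptake because it records sessions cut short. It covers only patients who were treated, so it cannot show those who received nothing.

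For 9.5, the natural reading is that eligibility comes before approval, and the screening form does record a screening status ahead of provider verification. This is fair: 9.5 is close to a sound definition. It still needs the word pinned down, because the plan's own forms use eligible in both senses.

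The 128% and 200% figures rest on consent rates quoted for eligible patients, applied here to approved ones. They are illustrations. That the ratio cannot fall below 100% does not depend on them.

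Finally, an adoption proportion over all presented patients will vary with case mix, because the sign-off form exists partly to exclude clinical conditions. That stands, and is why exclusions and unreturned forms need to be shown beside it. It is also true that the correct uptake can be recovered later from the same count once arm sizes are known; this limits the harm but leaves the definition wrong.

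**Conclusion.** The concern holds on both parts. Followed as written, 9.6 caps uptake at about 50% (48.0–52.0% if blocked within site) and roughly halves any true delivery rate. This rests on recruited meaning what Aim 2a, 9.5 and 6.2.2 make it mean, and on 1:1 allocation.

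The adoption denominators in 9.5 and 9.6 contradict each other. With recruited read as enrolled, the 9.6 prose is 100% by construction and the Table 1 ratio is at least 100%; neither reflects what providers did.

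The reach is limited to descriptive secondary outcomes with no decision threshold. The primary recruitment and retention outcomes and the sample size do not change. It should be corrected before analysis, so that the denominators are not chosen after the data are seen.

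**What to change.** - **Uptake (Table 1 and Aim 2b1):** completed sessions / patients randomised to acupuncture.
- **Adoption (9.5, Table 1 and the 9.6 prose, in identical words):** patients approved on the sign-off form / patients eligible on pre-screening (Section 2 of the Appendix B screening form) and presented to that provider for sign-off.
- **Alongside adoption:** report clinical exclusions and unreturned forms as separate counts, from the fields already in Section 3 of the screening form, so that they are not read as provider reluctance.

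The cost is two reworded definitions and some data linkage, with no new patients or procedures. The screening form holds no provider identifier, so identity can be taken from the signed sign-off forms. The Appendix B forms hold no completed-session item, so completion would come from the acupuncturists' session records and the single question already planned in Aim 2b1.

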10. DATA COLLECTION AND QUALITY ASSURANCE

10.1 Data Collection Forms

See attached RCT Data Collection Forms in **Appendix B**. Observation, Interview and Feasibility data collection sheets can be found in **Section 6.1**.

10.2 Data Management

In our pilot RCT, we developed and successfully used a basic electronic data collection tool (StudyTRAX). In Year 1, we will build a comprehensive study management database and data collection platform using REDCap and confirm the ability to blind assessors to patient scores and text message subjects for the 1-week follow-up assessment. Our team has successfully used REDCap for multisite data collection in the BraveNet PBRN as well as across [name] multi-clinic studies.

Informed consents and HIPAA authorizations will be collected as hard copy paper documents; these will be kept by the study team in individual patient binders in locked filing cabinets of a secure, badge-access location at each site.

Demographic and baseline data will be collected both by the SC and through EHR data extraction at baseline. The data collected by research staff will be entered directly into an electronic data collection tool. There will be no hard copies of this data.

Patient Reported Outcomes (PROs) (pain intensity and anxiety) will be collected by study staff (SC or RA), rather than by the acupuncturists delivering treatments. All PROs will be entered directly by the study participant on a tablet via REDCap and will disappear from view once entered so neither the participant nor research staff will have access to the scores. The scores will then be exported to a password protected database. There will be no hard copies of this data.

Satisfaction data will be collected as part of ED-discharge and at 1-week and 4-week follow up for patients. ED staff will complete a one-time brief survey at the end of the enrollment period.

EHR data will be electronically extracted by each site with HIPAA protected identifiers as limited datasets. The data extracted from EHR will be verified by MRN and date with our electronic platforms. EHR extracted data will include demographic data, pain medication use in the ED, and opioid prescriptions at discharge. Both [name] and [name] have extensive experience in use of EHR data. There will be no hard copies of this data.

1-week and 4-week follow-up data (PROs, pain medication/opioid use) will be collected either directly from the participant through the electronic data collection tool (via text message prompt) or collected on paper survey and entered by a member of the research team if the follow-up is completed over the phone. As above, all 1-week and 4-week contacts will be conducted by a research staff (SC or RA) who did not interact with the patient during their study participation in the ED.

All electronic data will be kept in password protected databases behind an electronic firewall at sites and then securely sent to the Einstein Coordinating Center and maintained on password protected PCs by a designated data manager. Data in hard copy form will be stored in locked file cabinets within a secure, badge-access location at each site. Upon completion of study enrollment, members of the study team will verify the information contained within the database. After answering all queries in the database, the information contained will be locked and exported for analysis. Both the source (electronic data collection) data and exported databases will be stored as required by the respective rules and regulations (e.g., HIPAA authorizations will be maintained for at least six years).

10.3 Quality Assurance

10.3.1 Training

The site Study Coordinator (SC) will ensure that all study personnel have completed all required

institution-specific and protocol-specific trainings and that these trainings are documented appropriately on the Training Log. The SC will also ensure that new personnel are appropriately documented on the Delegation of Responsibilities Log (DOR). While training should be completed and documented in real time, the Multi-Site Study Coordinator (MSC) will verify that all training is current and appropriately documented on a quarterly basis, as noted in section 10.3.2 below.

Institution-specific Training

All study staff will complete CITI or NIH Human Subjects training prior to commencement of study activities. The site staff is also required to receive Good Clinical Practice (GCP) training through CITI or the Society for Behavioral Health. Staff training certificates will be stored in the Regulatory Binder in REDCap and documented on the Training Log.

Protocol-specific Training

Below is a summary of required initial training by role for new study personnel.

PI, Study Coordinators, Research Assistants and anyone recruiting patients:

- ✓ Review and express understanding of the Site Initiation Visit (SIV) training slides
- ✓ Review and express understanding of the IRB protocol
- ✓ Review and express understanding of the NCCIH protocol
- ✓ Review and express understanding of the Informed Consents and Study Information Sheets
- ✓ Review and express understanding of the MOP

ED Physician and Students who are not recruiting patients:

- ✓ Review and express understanding of the IRB protocol
- ✓ Review and express understanding of the Informed Consents and Study Information Sheets

Statistician

- ✓ Review and express understanding of the IRB protocol

